SID	Subject identification number
UBACC	University of San Diego Brief Assessment of Capacity to Consent
UKCMC	University of Kentucky Chandler Medical Center

1. BACKGROUND

Atrial fibrillation (AF) is a common complication following cardiac surgery, occurring in approximately 33% of all patients after cardiac surgery. AF can sometimes cause a rapid ventricular rate (RVR), defined as a HR greater than 110 beats per minute (BPM). AF is typically characterized as either stable (systolic blood pressure (SBP) \geq 90 mmHg) or unstable (SBP <90 mmHg). Patients with unstable AF with or without RVR may require immediate electrical cardioversion to restore normal sinus rhythm (NSR) and an appropriate blood pressure; whereas, patients with stable AF frequently undergo medical therapy to either treat RVR or to restore NSR.

Amiodarone is a class III antiarrhythmic with beta-blocker activity that also blocks myocardial potassium, sodium and calcium channels. In stable AF, amiodarone is frequently given to control the HR and restore NSR after cardiac surgery. In this setting, amiodarone is commonly given as an initial intravenous (IV) bolus (150 mg IV) followed by a combined IV and oral load to a total dose of 8 gm. Because of amiodarone's beta-blocker activity, the IV bolus is associated with a reduced HR and may lead to restoration of NSR on its own. For this reason, some clinicians will provide up to 5 additional IV amiodarone boluses during the drug's loading period to treat RVR. Other clinicians will not specifically treat RVR in stable AF and will continue with the routine amiodarone IV and oral load. At this time, both dosing regimens are routinely used for patients after cardiac surgery, the decision to use one over the other is made based on clinician preference. It is not known whether the repeated amiodarone dosing regimen is better than the conventional amiodarone dosing regimen with regard to successful conversion to NSR or the time to conversion to NSR in patients with stable AF.

2. STUDY HYPOTHESIS

We hypothesize that, compared to a conventional dosing regimen (CDR), a repeated bolus dosing regimen (RBDR) of amiodarone will result in an increased percentage of patients who convert to normal sinus rhythm within 24 hours of initial AF.

3. OBJECTIVES

3.1 Primary Objective

The primary objective of this study is to compare, in patients who develop stable AF after nonemergent cardiac surgery, the percentage of patients who have converted to NSR at 24-hours after receiving a repeated amiodarone bolus and loading dose regimen to the percentage of patients who have converted to NSR after a conventional amiodarone IV loading dose regimen.

3.2 Secondary Objectives

The secondary objectives of this study are:

- Compare the total time, in minutes, during the first 24 hours that the patient achieves target HR (HR < 110 bpm) between patients who receive a repeated amiodarone bolus dosing regimen and those who receive a conventional amiodarone bolus dosing regimen.
- Compare the time to achieve target HR (HR < 110 bpm) between patients who receive a repeated amiodarone bolus dosing regimen and those who receive a conventional amiodarone bolus dosing regimen.

- Compare the time to achieve NSR between patients who receive a repeated amiodarone bolus dosing regimen and those who receive a conventional amiodarone bolus dosing regimen.
- Compare the percentage of patients who achieve NSR by ICU discharge and hospital discharge between patients who receive a repeated amiodarone bolus dosing regimen and those who receive a conventional amiodarone bolus dosing regimen.
- Compare the percentage of patients who have recurrent AF before ICU discharge and before hospital discharge between who patients who receive a repeated amiodarone bolus dosing regimen and those who receive a conventional amiodarone bolus dosing regimen.
- Compare the incidence and severity of hypotension between patients who receive a repeated amiodarone bolus dosing regimen and those who receive a conventional amiodarone bolus dosing regimen.
- Compare the incidence and severity of conduction abnormalities between patients who receive a repeated amiodarone bolus dosing regimen and in those who receive a conventional amiodarone bolus dosing regimen.
- Compare the incidence and severity of amiodarone-related pulmonary fibrosis between patients who receive a repeated amiodarone bolus dosing regimen and those who receive a conventional amiodarone bolus dosing regimen.

3.3 Exploratory Objectives

The exploratory objectives of this study are:

- Evaluate preoperative, intraoperative and postoperative factors that affect the efficacy of the amiodarone dosing strategy in achieving NSR at 24 hours, ICU discharge and hospital discharge.
- Evaluate preoperative, intraoperative and postoperative factors that affects the safety profile of the repeated amiodarone bolus dosing regimen.

4. STUDY DESIGN

This study is a single-center, prospective, randomized, open-label trial of subjects who develop AF after non-emergent cardiac surgery at the University of Kentucky Chandler Medical Center (UKCMC). Patients will be randomized to receive either a conventional amiodarone dosing regimen (CDR) or to a repeated amiodarone bolus dosing regimen (RBDR).

5. STUDY POPULATION

This study will include 150 patients undergoing non-emergent cardiac surgery. We anticipate approximately 60 of these patients will develop stable AF in the postoperative period. Patients will be \geq 18 years of age. The proposed dates of enrollment will be July 1, 2021 through June 30, 2023 or until full recruitment has been completed, whichever comes first.

5.1 Inclusion criteria

To be enrolled in this study, the subject must meet all of the following criteria:

- Subject must be ≥ 18 years old
- Subject must be willing to give written informed consent

• Subject must undergo non-emergent cardiac surgery, including coronary artery bypass grafting (CABG), non-infectious valve repair or replacement, atrial or septal defect repair, thoracic aortic replacement surgery or any combination of these procedures

5.2 Exclusion criteria

The subject will be excluded from the study if any of the following criteria are met:

- Documented allergy to amiodarone or iodine
- History of atrial fibrillation or other heart conduction system abnormality
- History of cardiac maze, pulmonary vein isolation, or other procedure affecting the conduction system
- Scheduled cardiac maze, pulmonary vein isolation, or other procedure affecting the conduction system
- Low cardiac index or cardiogenic shock requiring pharmacologic or mechanical support
- History of pre-existing respiratory system disease requiring oxygen therapy prior to admission
- History of cirrhosis or other chronic liver disease
- Pregnancy or breastfeeding mothers
- Prisoners

6. SUBJECT RECRUITMENT METHODS AND PRIVACY

Subjects will be screened and recruited in one of three ways.

First, potential subjects will be primarily screened in the Anesthesiology Preoperative Clinic and recruited by the PI or a member of the IRB-approved research team. These subjects will be consented for this study by the PI or a member of the IRB-approved research team during a scheduled clinic visit. The screening process will utilize ordinary standard of care procedures (e.g., medical evaluation, physical examination and diagnostic testing at the discretion of the attending cardiovascular surgeon and/or perioperative anesthesia team). Prior medical records documenting these evaluations, examinations and testing may be used as source documents for the baseline visit.

Second, because some patients may be hospitalized prior to their operation and will not present to the Anesthesiology Preoperative Clinic prior to their operation, hospitalized patients scheduled for surgery will be screened and consented using the above process prior to their operation.

Third, because some outpatients will not present to the Anesthesiology Preoperative Clinic and some inpatients will not be screened and consented prior to their operation, for a variety of reasons. These patients will be screened in the early postoperative period, after admission to the ICU. These patients will be recruited by the PI or a member of the IRB-approved research team. The screening process will utilize ordinary standard of care procedures (e.g., medical evaluation, physical examination and diagnostic testing at the discretion of the attending cardiovascular surgeon and/or perioperative anesthesia team). Prior medical records documenting these evaluations, examinations and testing may be used as source documents for the baseline visit.

Regardless of recruitment pathway, during the screening and recruitment process, the PI or another member of the research team will verify that the eligibility criteria have been met. Preoperative outpatients who meet the inclusion and exclusion criteria will be approached for informed consent. Inpatient preoperative and all postoperative patients who meet the inclusion and exclusion criteria will be further assessed for the continuous infusion of sedating agents. For these patients, the legally-authorized representative (LAR) will be approached for informed consent. For postoperative patients who meet the inclusion and exclusion criteria and are not receiving a continuous infusion of sedating agents, the University of San Diego Brief Assessment of Capacity to Consent (UBACC) test will be performed. For patients with a UBACC score of <18, the LAR will be approached for informed consent. For patients with a UBACC score of \geq 18, informed consent will be discussed with the patient. Written informed consent and a Health Insurance Portability and Accountability Act (HIPAA) authorization must be obtained prior to performance of any protocol-specific procedures.

7. ADVERTISING

None.

8. INFORMED CONSENT PROCESS

A full consent discussion will be held with the patient or legally-authorized representative LAR at which time the study protocol, procedures, risks/benefits, alternatives, and the voluntary nature of the research will be explained by the study staff. There will be an opportunity for the patient or LAR to ask questions and for private consideration/discussion with family, if needed. If the patient or LAR wishes to be involved in the protocol, study procedures will begin after the

patient's or LAR's signature is obtained on the informed consent and HIPAA documents. If the patient would like to take time outside the clinic visit to decide about enrollment, the patient may return the signed consent to their next visit, including preoperatively on the day of surgery. For patients who have LAR consent and are no longer on continuous infusions of sedation and who regain consciousness and their UBACC score improves to \geq 18, the patient themselves will be re-consented using the process and procedures previously described. No study procedures will begin until after the signed copy of the informed consent and HIPAA documents are obtained. A note in the patient file will be written explaining how the patient meets study criteria, the process of informed consent and the nature of the discussion, and who participated in the consent process. This note will be generated by the PI or another member of the study team.

9. RESEARCH PROCEDURES

All enrolled patients will receive the standard of care perioperative institutional protocol for their cardiac surgical procedure. The preoperative and intraoperative management will be performed at the discretion of the cardiovascular surgery team, the anesthesia team, and other healthcare teams. The postoperative management will be performed at the discretion of the cardiovascular surgery team and the consultant anesthesiology critical care team according to standard management protocols.

As part of standard postoperative management, all patients will undergo continuous electrocardiographic (ECG) monitoring in the postoperative period. If new AF is identified within the first 72 hours after they are admitted to ICU following their surgical procedure, the patient will be assessed for hemodynamic stability. If the patient is unstable (SBP <90 mmHg)

or requires a significant increase in vasopressor infusion (an increase of more than 1.5x in baseline infusion rate) to maintain SBP>90 mmHg, the standard of care patient management will be provided and the patient will not be randomized to either study group. If the patient is stable (SBP>90 mmHg and requires less than 1.5x more vasopressor infusion to maintain SBP>90 mmHg), the patient will be given up to 15 mg IV metoprolol, in divided doses, and monitored for 20 minutes for conversion to NSR. If stable AF persists, the patient will be randomized according to the plan described below to either the conventional amiodarone dosing regimen (CDR) or to the repeated amiodarone bolus dosing regimen (RBDR).

Patients in both groups will receive an amiodarone bolus of 150 mg IV over 10 minutes then a 24-hour amiodarone loading infusion (1 mg/min for 6 hours followed by 0.5 mg/min for 18 hours). After these infusions have been completed, patients in both groups will receive additional enteral (400 mg amiodarone oral or per tube three times daily or 2 times daily if the patient has gastrointestinal intolerance when taking the drug three times daily) or intravenous amiodarone (0.5 mg/min continuous infusion) to complete an 8-gm total amiodarone load. After the amiodarone load is completed, patients in both groups will receive maintenance amiodarone (200 mg amiodarone oral or per tube once daily). Further management of amiodarone dosing will be at the discretion of the attending cardiac surgeon, critical care medicine specialist or cardiologist. Other medications will be at the discretion of the attending cardiac surgeon, critical care medicine specialist or cardiologist. Patients will be monitored continuously throughout the 24-hour amiodarone IV load time period according to standard protocol.

9.1 Conventional Dosing Regimen (CDR)

Patients randomized to the CDR group will receive the previously-described amiodarone bolus followed by a 1.0 mg/min IV amiodarone infusion for 6 hours and then a 0.5 mg/min IV amiodarone infusion for 18 hours.

9.2 Repeated Bolus Dosing Regimen (RBDR)

Patients randomized to the RBDR group will receive the previously-described amiodarone bolus followed by a 1.0 mg/min IV amiodarone infusion for 6 hours and then a 0.5 mg/min IV amiodarone infusion for 18 hours. In addition, patients in the RBDR will receive an additional 150 mg IV amiodarone bolus whenever the patient develops tachycardia (Heart Rate (HR) \geq 110 beats per minute) lasting more than 10 minutes. This bolus may be repeated up to a total of 5 times (6 total boluses) over the first 24 hours.

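### Section 9.2 triggers repeat amiodarone boluses on a sustained heart rate, without requiring that the patient is in AF or still hemodynamically stable

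*Protocol*

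**What the plan says.** Under Protocol Section 9.2, RBDR patients "will receive an additional 150 mg IV amiodarone bolus whenever the patient develops tachycardia". Tachycardia there means a heart rate of at least 110 bpm for more than 10 minutes. The cap is five repeats, six boluses in all, over the first 24 hours.

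Three other places bear on this rule:

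- **Purpose.** Section 1 describes rapid ventricular rate (RVR) as something AF causes, and reports that some clinicians give "up to 5 additional IV amiodarone boluses during the drug's loading period to treat RVR".
- **Instability.** Section 1 also says "Patients with unstable AF with or without RVR may require immediate electrical cardioversion to restore normal sinus rhythm (NSR) and an appropriate blood pressure". Section 9 tests stability when AF is first found, using systolic pressure and the change in vasopressor rate. For an unstable patient, "the standard of care patient management will be provided and the patient will not be randomized to either study group".
- **Discretion.** Section 9 says "The postoperative management will be performed at the discretion of the cardiovascular surgery team and the consultant anesthesiology critical care team", and later "Further management of amiodarone dosing will be at the discretion of the attending cardiac surgeon, critical care medicine specialist or cardiologist". Section 12 makes the critical care team responsible for ordering study drugs under its usual protocols and for responding to unexpected reactions.

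The SAP repeats the analysis section and adds nothing on dosing.

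**The concern.** The rule that decides who gets more drug leaves out two conditions that the protocol relies on elsewhere: that the fast rate is due to AF, and that the patient is stable. Both can change within the 24-hour window. Conversion is the primary outcome, so some trigger time will be spent in sinus rhythm. Hypotension is described in Section 21 as an expected complication of amiodarone.

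Two things are at stake.

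- **Patient safety.** A patient with a heart rate of 120 and a systolic pressure of 80 meets the trigger. A further bolus could deepen the hypotension and move the patient up the Section 10.3 severity scale, which Section 11.3 compares between arms.
- **Definition of the regimen.** Without a stated criterion, clinicians may hold at different thresholds. Nothing says whether a held bolus is RBDR as intended or a deviation from it.

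**Working it through.** The documents state no figure for this point, so the check is mainly one of text, with dose arithmetic to bound the size.

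**Step 1. Where AF and stability are required**

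| Place | What it does | Governs repeat boluses? |
|---|---|---|
| Section 1 | Links RVR to AF; gives RVR as the target of repeat boluses | No, background only |
| Section 9 | Tests stability, then persistence of AF after metoprolol | No, gate to randomization |
| Section 9.2 | Heart rate, duration, cap of five | Yes, but no rhythm or pressure condition |
| Section 9.4 | Persistent, stable AF leads to randomization and treatment | Ambiguous (see objection) |
| Section 10.3 | Records hypotension, bradycardia and conduction abnormality during the IV load | No, outcomes only |
| Section 21 | Grades events as AE or SAE; reviews after the first 10 patients and then every 20 | No, study-level decision after patients finish |

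Section 10.3 defines hypotension in nearly the same terms that Section 9 uses for instability: systolic pressure below 90 mmHg, or a 1.5x vasopressor increase. So a state that bars randomization is, once the patient is randomized, recorded without any dosing action.

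**Step 2. Dose ceiling**

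Inputs from Sections 9 and 9.2: initial bolus 150 mg; infusion 1 mg/min for 6 h, then 0.5 mg/min for 18 h; up to five repeats of 150 mg.

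- Infusion, both arms: 1 × 360 + 0.5 × 1,080 = 360 + 540 = 900 mg.
- CDR over 24 hours: 900 + 150 = 1,050 mg.
- RBDR maximum: 1,050 + 5 × 150 = 1,800 mg.
- Excess: 1,800 − 1,050 = 750 mg, and 750 / 1,050 = 71%.

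A patient who becomes hypotensive after bolus k can still qualify for (6 − k) × 150 mg:

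| k | Remaining dose (mg) | Share of 1,050 mg |
|---|---|---|
| 1 | 750 | 71% |
| 2 | 600 | 57% |
| 3 | 450 | 43% |
| 4 | 300 | 29% |
| 5 | 150 | 14% |

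The top row is simply the full excess that RBDR is designed to allow. It is reached only if hypotension follows the first bolus, the trigger is met five more times, and nobody intervenes.

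**The case against.** The best defense is delegation. Patients are monitored continuously during the IV load, experienced teams order the drugs under institutional protocols, and Section 9.2 itself uses permissive wording for the repeats. Those institutional protocols are not among the documents and may contain a hold threshold. Section 13 says both regimens are already used by clinician preference, so leaving holds to clinicians is a defensible pragmatic choice. Section 9.4 can also be read as making persistent, stable AF a condition of treatment as well as of randomization.

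Much of this stands as a prediction of what would happen: a bolus would often be held in an obviously hypotensive patient. It does not repair the rule. The clause on further amiodarone management follows the maintenance-dose sentence and reads most naturally as care after the load. Section 12 speaks of unexpected reactions, whereas Section 21 calls hypotension expected. The permissive wording sets the cap; the instruction to give the bolus is mandatory. Section 9.4 is too ambiguous to settle the matter. None of these places gives a criterion or says how a hold is to be classed.

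A reader might infer more than the documents support:

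- **That missing holds are a problem of RBDR only.** The 900 mg infusion in both arms also has no written hold for hypotension. Only the bolus-specific excess is confined to RBDR.
- **That a known number of patients would be affected.** The documents give no rate at which patients meet the trigger while hypotensive or in sinus tachycardia, so none can be calculated.
- **That any new vasopressor should bar further boluses.** Section 9 defines instability by an increase over the baseline infusion rate. Counting every vasopressor start goes further, and could deny boluses to a patient in fast AF whose pressure is adequate.

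**Conclusion.** The point holds. The repeat-bolus trigger is mis-specified against the protocol's own purpose and stability test: followed literally, it doses patients in sinus tachycardia and patients who have become hypotensive. The dose at issue is bounded by 750 mg over the 1,050 mg CDR dose, and is smaller the later the hypotension appears. How often this would happen cannot be estimated from the documents.

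The conclusion rests on the sections supplied and on reading Section 9.2 as the operative instruction. It does not assume that clinicians would give a bolus regardless of blood pressure.

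It would be wrong to conclude that the trial's main result is compromised. The randomized 24-hour sinus rhythm comparison remains a valid comparison of the regimens as delivered. What suffers is the safety of individual RBDR patients and the precision with which the tested regimen is described. That justifies a correction to the protocol but no change to the analysis.

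**What to change.** Amend the trigger in Section 9.2 along these lines:

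*Give a further 150 mg bolus when the patient is in AF with a heart rate of 110 bpm or more for over 10 minutes and still meets the Section 9 stability criterion (SBP at or above 90 mmHg without a vasopressor increase of more than 1.5x). Otherwise hold repeat boluses and give standard care until the criterion is met again. Such a hold is part of the assigned RBDR regimen.*

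The cap of five and the 24-hour window stay as they are. Using at or above 90 mmHg follows Section 1 and settles a systolic pressure of exactly 90, which Section 9 classes as neither stable nor unstable.

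The cost is modest. Some RBDR patients will receive fewer or later boluses, so the dose contrast with CDR becomes somewhat smaller. Holds will need to be recorded: Section 10.3 lists the total bolus count and hourly heart rate, but not rhythm or blood pressure at each trigger, nor any held bolus. Section 10 says its list is not exhaustive, so a short entry can be added. The change does not address the infusion, for which the sponsor may want a parallel hold rule in both arms.

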9.3 Informed Consent

The PI or another study team member will explain the study to the subject, answer all of the subject's questions, and obtain written informed consent before the collection of any study data or performance of any study-related procedures.

The subject must be willing and able to sign and date the informed consent form (ICF) prior to the collection of any study-related data. The original, signed informed consent will be retained with the subjects' records and a copy provided to the subject.

